6.10.2.2. Analysis of Immunogenicity Related to Covid-19 Vaccination

Missing and/or Unquantifiable Immune Response Data: Details in Section 6.14.6.

A demographic table of study participants who received Covid-19 vaccination will be provided including:

- number and percentage of subjects having pre-vaccination antibody assessment
- number and percentage of subjects having post-1st vaccine regimen assessment
- number and percentage of subjects having both pre- and post- 1st vaccine regiment assessment
- number and percentage of subjects having post-1st booster assessment
- number and percentage of subjects having post-2nd booster assessment
- number and percentage of subjects having post-3rd booster assessment
- age at time of vaccination
- sex
- exposure (years) to ponesimod at time of first vaccination
- time interval (days) between 1st dose of vaccine and post-1st vaccination sample
- number and percentage of subjects in different vaccine type of the 1st vaccine regimen
- number and percentage of subjects with or without evidence of prior Covid-19 infection
- number and percentage of subjects in different categories of lymphocyte count

In the above frequency tabulations, percentage is calculated based on number of patients in Covid-19 Vaccinated Set.

For S-ELISA, N-ELISA, and wild type VNA assays, the following results will be presented:

- N, geometric mean and corresponding 95% CI of the actual values of pre-vaccination, postfirst vaccine regimen, post first booster and post second booster.
- For participants with pre- and post-vaccination assessments, fold increases in comparison to baseline (geometric mean, 95% CI) will be presented for post-1st vaccine regimen, post-1st booster, post-2nd booster and post-3rd booster. Note that the analysis for post-2nd and post-3rd booster will be performed only if there are > 5 datapoints.
- Number of responders (percent and 95% CI) at post-1st vaccine regimen assessment will be tabulated.

- Dot plots with dots for participant values with the corresponding geometric mean, 95% CI, minimum and maximum for each assay, for pre-, post-1st vaccine regimen, post-1st booster, post-2nd booster and post-3rd booster will be presented. In the graphs, values in BAU/ml unit will be displayed on the log10 scale. Note that the analysis for post- 2nd booster and post- 3rd booster will be performed only if there are >5 datapoints.
- The analyses of the first three bullets will be repeated for S-ELISA antibody concentrations for the following subgroups: vaccine type of the 1st vaccine regimen, evidence of prior Covid-19 infection and categories of lymphocyte count. Box plot will be generated to visualize S-ELISA antibody concentrations for the above-mentioned subgroups. Note that for each booster timepoint, the subgroup analyses will be done only if >= 10 datapoints are available post each booster.

Analyses of S-ELISA and N-ELISA antibody concentration will be presented in BAU/ml unit only. Analyses of wild type VNA assays will be presented in original unit only.

For the calculation of the geometric mean and its corresponding 95% CI, the arithmetic mean and its corresponding 95% CI are calculated on the log10 transformed values. These values are back-transformed to provide the geometric mean and its corresponding 95% CI.

A listing containing assessment date, timepoint related to each vaccination and value of S-ELISA, N-ELISA and wild type VNA assessment antibody concentration will be provided. A listing of Covid-19 vaccinations will be provided.

6.10.3. Analysis of Adverse Events Related to Covid-19 Vaccination

A summary table will be provided for the following Covid-19 infection AEs for the Covid-19 VaccinatedSet:

- (i) any Covid-19 infection AEs.
- (ii) any Covid-19 infection serious AEs.
- (iii) any Covid-19 infection AEs sorted by severity (mild, moderate, severe).
- (iv) any Covid-19 infection AEs leading to treatment interruption.
- (v) any Covid-19 infection AEs leading to treatment discontinuation.
- (vi) any Covid-19 infection AE leading to death.

For each of the above, summary tables will include overall, and the following time-points:

- (vii) any Covid-19 infection AEs prior to 1st dose of vaccination
- (viii) any Covid-19 infection AE post 1st dose (Day 1) of vaccination
- (ix) any Covid-19 infection AE with onset at least 14 days (Day 15) post-vaccination (1st dose of any Covid-19 vaccination)
- (x) any Covid-19 infection AE with onset at least 28 days (Day 29) post-vaccination (1st dose of any Covid-19 vaccination)

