6.9. Appendix 9 Medications of Special Interest

6.10. Appendix 10 Covid-19 Analyses

This appendix describes the analyses and presentation of immunogenicity and clinical endpoints for objectives related to the assessment of immune response to Covid-19 vaccination in participants in the AC-058B202 study.

Specific objectives are:

- To describe binding antibody concentrations to SARS-CoV-2 S protein as measured by Enzyme-linked immunosorbent assay (ELISA)
- To describe binding antibody concentrations to SARS-CoV-2 N protein as measured by ELISA
- To describe SARS-CoV-2 neutralization as assessed by SARS-CoV-2 neutralization assays VNA (wild-type virus neutralization assay (wtVNA))
- To describe Covid-19 vaccine responders as assessed by binding antibody concentrations to SARS-CoV-2 S protein.
- To describe Covid-19 infection Adverse events (AEs).

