6.10.1. Immunogenicity Variables

Patients receiving non-live vaccinations while on study treatment will have 5 mL of blood drawn prior to and at least 3 weeks after vaccination to explore changes in vaccine-specific antibody titers from pre- to post-vaccination.

For Covid-19 vaccination, the following humoral immune response parameters are measured, including titers of neutralizing antibodies, S- and N-ELISA titers, and S- and N-ELISA positivity.

Humoral Assay	Purpose
SARS-CoV-2 binding antibodies to S protein	Analysis of antibodies binding to SARS-
(ELISA)	CoV-2 S protein
SARS-CoV-2 seroconversion based on	Analysis of antibodies binding to SARS-
antibodies to N protein (ELISA)	CoV-2 N protein
SARS-CoV-2 neutralization (wtVNA)	Analysis of neutralizing antibodies to the
	wild-type virus

 Table 14:
 Types of SARS-CoV-2 Antibodies

6.10.2. Analysis of Immunogenicity Related to Covid-19 Vaccination:

6.10.2.1. Analysis related definitions:

Baseline: The baseline for Covid-19 vaccine analyses is defined as the last pre-vaccination assessment. For participants missing a pre-vaccination assessment, summaries will be restricted to post-vaccination results only, where applicable.

Analysis Set: The Covid-19 Vaccinated Set (CVAS) is defined as all subjects in the PAS who reported receiving at least 1 dose of any Covid-19 vaccine.

Covid-19 vaccines are selected from the SDTM.CM data as described in Section 6.5.

First Vaccine Regimen: For each subject, the 1st and 2nd doses of vaccine in the SDTM CM dataset are considered. Definition of 1st Vaccine Regimen for Janssen vaccine: Only the 1st dose is considered.

First Booster: The 1st subsequent dose of vaccine after first vaccine regimen is considered as the First Booster.

Second Booster: The 2nd subsequent dose of vaccine after first vaccine regimen is considered as the Second Booster.

Lymphocyte count linked to a specific vaccination will be determined as the minimum of the last two available values within six months prior to the first vaccination date for a given participant. If only one value is available within this time range, this value will be used. If none is available in the range, the lymphocyte count value corresponding to the particular vaccination will be considered missing. Categories of "Lymphocyte Count < 500 mm³" and "Lymphocyte Count >= 500 mm³" will be used in the analysis.

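### The only Covid-19 adverse event table split by vaccination (SAP 6.10.3) is limited to vaccinated subjects and has no time at risk, so deaths before any dose cannot appear and its pre- and post-dose counts are not comparable

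*SAP*

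**What the plan says.** SAP 6.10.3 plans one summary: "A summary table will be provided for the following Covid-19 infection AEs for the Covid-19 VaccinatedSet". Rows (i) to (vi) cover any infection event, serious events, events by severity, events leading to interruption or discontinuation of treatment, and "vi) any Covid-19 infection AE leading to death".

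The rows are crossed with time: "For each of the above, summary tables will include overall, and the following time-points". The first time-point is "any Covid-19 infection AEs prior to 1st dose of vaccination". The next is "viii) any Covid-19 infection AE post 1st dose (Day 1) of vaccination", followed by onset from Day 15 and onset from Day 29.

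The population is defined in SAP 6.10.2.1: "The Covid-19 Vaccinated Set (CVAS) is defined as all subjects in the PAS who reported receiving at least 1 dose of any Covid-19 vaccine". Section 6.10.3 gives no start or end for any window and no observation time. The stated objective in SAP 6.10 is only to describe Covid-19 infection adverse events, and SAP section 2 makes all objectives exploratory.

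**The concern.** Membership of the analysis set depends on an event, vaccination, that comes after the period shown in the first column. To contribute to the pre-dose column a subject must have survived, and stayed under observation, until a dose was recorded. That is conditioning on the future: the pre-dose period is immortal time for anyone in the table. The worst pre-dose outcomes are the ones removed.

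The pre- and post-dose columns also cover different lengths of follow-up, and the three post-dose columns overlap. A reader who sees deaths, serious events and discontinuations laid out before and after vaccination will tend to compare them, and nothing in the table makes that valid. The drug lowers circulating lymphocyte counts (Protocol 1.3.2.2), so severe Covid-19 before vaccination is an outcome a reader would look for here.

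**Working it through.** The plan states no sample size, event count or rate for this table, so there is no figure to reproduce. The check is partly logical and partly person-time arithmetic on assumed dates.

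**1. Deaths before any dose.** Entry requires a recorded dose (6.10.2.1). A subject who dies with no dose has none, so the number of such deaths in the table is 0 whatever the truth. To show what can be hidden, assume a constant infection hazard h per year, fatality c, first dose 1.5 years after the pandemic start, end of follow-up at 3.5 years, no vaccine effect, and everyone alive at 1.5 years vaccinated.

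- True pre-dose deaths per 1000 = 1000 × c × (1 − exp(−1.5h)).
- h = 0.05, c = 0.01: 1000 × 0.01 × 0.0723 = 0.7.
- h = 0.20, c = 0.05: 1000 × 0.05 × 0.2592 = 13.0.
- A simulation of the same set-up gave 0.7 and 12.8 per 1000. The vaccinated-set table showed 0 in every scenario, beside 0.97 to 12.4 post-dose deaths per 1000.

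One exception: a fatal event with onset before a dose given during the illness could fall in the fatal/pre-dose cell. The exact zero applies to deaths that occur before any dose.

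**2. Pre-dose discontinuations.** Concomitant medications are recorded until end of study (Protocol 3.11.5.3). For subjects in treatment periods 2 and 3 that is 90 days after the last dose (Protocol 3.1.1). A subject who stops drug for Covid-19 while unvaccinated enters the table only if a vaccine dose is recorded within that window. The row is depleted. The documents do not allow the amount to be estimated.

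**3. Time at risk.** With a constant hazard and no vaccine effect, expected post/pre event ratio = (end of follow-up − first dose) ÷ (first dose − 1 January 2020). The start is the pandemic date in SAP 5.5.8. Dose and end dates are assumptions; the protocol synopsis plans the last visit for Q4 2023.

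| First dose | Years before | End 1 Jul 2022: years after, ratio | End 31 Dec 2023: years after, ratio |
|---|---|---|---|
| 1 Jan 2021 | 1.00 | 1.49, 1.49 | 3.00, 2.99 |
| 1 Jul 2021 | 1.50 | 1.00, 0.67 | 2.50, 1.67 |
| 1 Jan 2022 | 2.00 | 0.50, 0.25 | 2.00, 1.00 |

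The share of events falling after the first dose is ratio ÷ (1 + ratio): 0.25/1.25 = 20% to 2.99/3.99 = 75%.

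**4. Nested columns.** Onset from Day 15 and from Day 29 are subsets of onset from Day 1. For a first dose on 1 January 2021 and follow-up to 1 July 2022, the three ratios to the pre-dose period are 1.49, 1.45 and 1.42. The columns largely repeat one another.

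**5. Whether other outputs fill the gap.** SAP 5.4.4.1 puts adverse event summaries on the PAS by default. Covid-19 terms in never-vaccinated subjects therefore enter the treatment-emergent tables as frequencies and per 100 subject-years (5.4.4.3.2), the serious event tables (5.4.4.4.2), the discontinuation table (5.4.4.4.3) and deaths by cause (5.4.4.4.1). None is split by vaccination. The denominator in 5.4.4.2 runs from ponesimod start. Extension entry closed in Q2 2011 (Protocol synopsis), so a subject still on drug on 1 January 2020 brings roughly 8.5 years or more that predate the pandemic, apart from pregnancy interruptions. At most about 4.0 years can follow by the end of 2023. Even then pandemic time is only 4.0/(8.5 + 4.0) = 32% of that subject's total, so a Covid-19 rate on this denominator is heavily diluted.

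**The case against.** The strongest reply is that this is a supplementary table in an appendix about immune response to vaccination. The vaccinated set is the natural population for asking which vaccinated subjects had Covid-19 before or after dosing, and prior infection is itself a subgroup in the immunogenicity analysis. The plan contains no rate ratio, interval or test comparing the periods. Overall Covid-19 risk is left to the PAS safety tables, where a death before vaccination is tabulated by cause and listed. Rates split at vaccination would still be confounded by calendar time, because unvaccinated and vaccinated follow-up fall in different phases of the pandemic.

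Much of this stands, and it rules out several stronger readings:

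- A reader might infer that Covid-19 events are tabulated only in vaccinated subjects and never with person-time. That is wrong for the SAP as a whole.
- A reader might infer that the plan will make vaccination look less protective, or will understate risk on ponesimod. Those are conclusions someone could draw from the layout; the plan does not draw them.
- A reader might expect pre-dose discontinuations to be close to zero. Stopping treatment is not leaving the study (SAP 5.2.1.6), a dose during follow-up still counts, and no figure supports that expectation.
- A reader might expect most events to fall after vaccination. Under later vaccination or earlier exit, most would fall before it.

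What the reply does not answer is that the table asks for a pre-dose fatal cell that cannot record deaths before any dose, carries no label saying so, and sets counts over undefined and unequal periods side by side. No other planned output shows Covid-19 outcomes by vaccination status.

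**Conclusion.** The point holds for the 6.10.3 table. Three parts follow from the definitions alone and need no assumption: deaths before any dose cannot appear, never-vaccinated subjects are absent, and the post-dose columns are nested. Depletion of pre-dose discontinuations follows from the recording window, but its size is unknown. Non-comparability of the pre- and post-dose counts follows from the lack of any time at risk. The ratio range of 0.25 to 2.99 illustrates it and rests on assumed dose and end dates and a constant infection rate.

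Severity is minor to moderate. The analysis is descriptive and exploratory, and Covid-19 events and deaths in unvaccinated subjects are reported elsewhere, though not by vaccination status and not over pandemic time.

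**What to change.** Produce the 6.10.3 table on PAS subjects under observation on or after a stated pandemic start, for example 1 January 2020 as in SAP 5.5.8. State when observation ends.

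- Classify follow-up as unvaccinated (including never-vaccinated subjects) or after the first dose. Keep the SAP's cut-points as non-overlapping periods: Days 1 to 14, Days 15 to 28, and Day 29 onward.
- For each of rows (i) to (vi), report events, subject-years and the rate per 100 subject-years, which is already the SAP's convention in 5.4.4.2. State whether fatal events are placed by onset date or date of death.
- Footnote that the periods differ in calendar time and that no vaccine-effect inference is intended.
- Keep the Covid-19 Vaccinated Set for the immunogenicity analyses.

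The cost is a change of wording and the reprogramming of one table. Vaccination, adverse event and disposition dates are already in the CM, AE and DS datasets, so no new data are needed. The rates will remain confounded by calendar time, which is why the footnote belongs with them.

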6.11. Appendix 11 Influenza Analyses

Seasonal influenza vaccine typically contains killed strains of Influenza type A and influenza type B. For subjects who have been administered seasonal influenza vaccine, antibody titers against influenza vaccine will be measured by hemagglutination inhibition (HAI) antibody titer (hemagglutination test) by ELISA.

The administration of influenza vaccine is stored in SDTM CM dataset (variable CMCLAS="INFLUENZA VACCINES"). The antibody titers concentration triggered by influenza vaccine(s) are stored in SDTM LB dataset.

The first documented influenza vaccine in the dataset is defined as "1st vaccination". For subjects with multiple influenza vaccinations over years, the subsequent doses are defined as "2nd vaccination", "3rd vaccination", "4th vaccination", etc.

Identification of vaccination sequence and antibody concentrations related to each vaccination:

As the doses are not labeled in the dataset, determination of the vaccination doses will be based on a combined assessment of the influenza vaccination dates, as follows:

- The sequence of vaccination and sample collection dates will be ordered.
- Only the samples assessed within 183 days prior to each vaccination are considered as prevaccination assessment. Only the samples assessed within 183 days on or after each vaccination are considered post-vaccination assessment. If the time frame between 2 vaccinations is less than 366 days the time frame for: Before vaccination to the subsequent vaccination is reduced respectively" (We will look 183 before and after a vaccination to assign "Pre"/"Post". In case the time between 2 vaccinations is less than 366 days the described rule was used).
- The nearest sample preceding the 1st dose will be considered "Pre-1st Vaccination". The same logic is used for detecting the sample for "Pre-2nd vaccination", "Pre-3rd vaccination", "Pre-4th vaccination", etc.
- The sample following the 1st dose and preceding the 2nd dose will be considered "**Post-1st Vaccination**". In case there are multiple in this interval, the sample closest to 1st vaccination is considered. The same logic is applied to detect sample for "Post-2nd vaccination", "Post-3rd vaccination", "Post-4th vaccination", etc.

The following immunogenicity analysis related to influenza vaccine will be conducted:

- A listing will be provided to include influenza antibody concentration information.

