3.4.4.2 Allowed concomitant medications

Administration of intravenous (i.v.) atropine in the event of symptomatic bradycardia.

Vaccination with non-live vaccines is allowed while on study treatment if the vaccination is advised by the primary investigator / treating neurologist, based on her/his clinical assessment of the risk/benefit for the individual patient, and if supported by guidelines for vaccination relevant to this patient population, as applicable.

Ponesimod / ACT-128800 / JNJ-67896153 Multiple Sclerosis		EudraCT 2009-011470-15 EDMS-ERI-206617631
Protocol AC-058B202	Confidential	
Version 12		
15 March 2022, page 63/179		

Patients receiving non-live vaccination against influenza or COVID-19 while on study treatment will have 5 mL of blood drawn prior to and at least 3 weeks after vaccination in order to explore changes in vaccine-specific antibody titers from pre- to post vaccination. Samples will be analyzed at the end of the study at the latest. In case of a vaccine requiring the administration of multiple doses, the post-vaccination sample should be collected at least 3 weeks after the administration of the last dose.

Glatiramer acetate and IFN β -1a are allowed only during study drug interruptions for planned pregnancy. These treatments may be started 7 days after study drug interruption and must be stopped 7 days before study drug re-initiation.

Low dose of corticosteroids (up to 10 mg of prednisone equivalent daily), given as shortterm treatment (up to 2 weeks per treatment cycle with at least 8 weeks' interval between treatment cycles and no more than 4 weeks per year of the study duration on average), and inhaled corticosteroids for pulmonary conditions.

Other treatments considered necessary for the patient's benefit and not categorized as prohibited concomitant medications.

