 - Categorical change from baseline to all assessments in EDSS and FS scores.
- 7. Ophthalmological endpoints:
 - Change from baseline to all assessments of average retinal nerve fiber layer (RNFL) thickness, central foveal thickness and total macular volume as measured by optical coherence tomography (OCT) at selected centers.
 - Change from baseline to all assessments of average number of letters correctly read in a best corrected visual acuity test (recorded only at the centers that also perform OCT).
- 8. Changes in vaccine-specific antibody titers from pre- to post vaccination will be explored at the end of the study, at the latest, for patients having received non-live vaccination against influenza or COVID-19 while in the study.

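### SAP 6.11 can label a same-day pre-dose influenza sample as Post and select it over the protocol's 3-week sample, and it gives endpoint 8 no derived influenza result

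*SAP*

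**What the plan says.** Protocol 3.4.4.2 states that patients who receive a non-live influenza or COVID-19 vaccine on study treatment "will have 5 mL of blood drawn prior to and at least 3 weeks after vaccination". Protocol 3.11.2.9.1 and 3.11.2.9.2 repeat this. No minimum gap is set between the first draw and the injection, so a draw on the vaccination day, before the dose, complies. Endpoint 8 in Protocol 3.10.1 is the titre change: "Changes in vaccine-specific antibody titers from pre- to post vaccination will be explored at the end of the study".

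SAP 6.11 sets out how influenza samples are matched to doses:

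- Ordering: "The sequence of vaccination and sample collection dates will be ordered".
- Pre window: "Only the samples assessed within 183 days prior to each vaccination are considered as prevaccination assessment".
- Post window: "Only the samples assessed within 183 days on or after each vaccination are considered post-vaccination assessment".
- Pre selection: "The nearest sample preceding the 1st dose will be considered" the pre-vaccination value.
- Post selection: the sample *following* the dose and *preceding* the next one; "In case there are multiple in this interval, the sample closest to 1st vaccination is considered". The same logic is applied to later vaccinations.
- Output: "A listing will be provided to include influenza antibody concentration information". No other influenza analysis is described.

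SAP 6.2.1 says that the influenza appendix was added to address endpoint 8.

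**The concern.** The post window includes the vaccination date and the pre window does not name it. A sample drawn that morning before the injection therefore falls into Post. Being zero days from the dose, it is also the closest candidate and is selected over the sample taken 3 or more weeks later. Nothing in SAP 6.11 looks at clock time or at the planned-timepoint label, and the protocol's 3-week minimum does not appear.

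The SAP guards against this kind of error elsewhere. Section 5.1.2 uses assessment time, where available, to settle the baseline among assessments on the first-dose date. Section 5.1.4 exempts same-day assessments that are clearly documented as pre-dose from the treatment-emergent class. Section 6.10.2.1 uses the planned timepoint when a lone COVID-19 sample between two doses could be either post or pre.

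At stake is whether a reader of the influenza listing can rely on its Pre and Post assignments. With no influenza summary planned, those assignments are the only route to endpoint 8 for influenza.

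**Working it through.** There is no stated figure to reproduce and no sample-size or power calculation involved. The check is to apply the SAP 6.11 rule to plausible sample dates.

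**Inputs.** Days are counted from vaccination, with the vaccination date as Day 0.

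- Rule as written (SAP 6.11): Pre = nearest sample from Day -183 to Day -1; Post = nearest sample from Day 0 to Day 183.
- Protocol schedule (3.4.4.2): one draw before vaccination and one at Day 21 or later.
- Titres are illustrative assumptions, not document figures: 10 just before the dose, 12 at an older draw, 20 at Day 7, 80 at Day 21. The correct ratio is therefore 80/10 = 8.0 in every case.

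**Rule as written.**

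| Case | Samples drawn | Pre chosen | Post chosen | Ratio if someone formed it |
|---|---|---|---|---|
| A | Day 0 (pre-dose), Day 21 | none | Day 0 | cannot be formed |
| B | Day -1, Day 21 | Day -1 | Day 21 | 80/10 = 8.0 |
| C | Day -84, Day 0 (pre-dose), Day 21 | Day -84 | Day 0 | 10/12 = 0.83 |
| D | Day -1, Day 7, Day 21 | Day -1 | Day 7 | 20/10 = 2.0 |

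The rule works when the pre-dose draw is on an earlier day and there is no early extra draw (B). With only the two protocol samples and a same-day draw, the pair is lost rather than distorted (A). A wrong value from a same-day draw needs a third, older sample within 183 days (C). Case D does not depend on same-day draws; it arises because there is no 3-week floor.

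**How readily case C could occur.** If influenza vaccination is roughly yearly (an assumption), the 3-week sample from the previous season is about 365 - 21 = 344 days old at the next dose. That is outside the 183-day window, so the previous season's scheduled sample would not normally fill the gap.

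**Effect of repairs.**

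1. Day 0 counted as Pre, with Post strictly after Day 0: A and C both give Pre = Day 0, Post = Day 21, ratio 8.0. D still selects Day 7, ratio 2.0.
2. Repair 1 plus Post at Day 21 or later: all four cases give Post = Day 21 and ratio 8.0.

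Both changes are therefore needed.

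**Wording within SAP 6.11.** The window bullet gives Day 0 to Post. The selection bullets speak of samples preceding and following the dose, and a draw taken before the injection does precede it. Two programmers could label the same sample differently and each cite the text.

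**The case against.** The strongest objection is that no planned influenza result can go wrong. A reader might infer that the influenza titre change will be miscalculated, or that the data will falsely suggest no vaccine response on ponesimod. The documents do not support either inference: the only planned output is a listing, no change or geometric mean is computed, and with the two protocol samples a derived change would be missing rather than wrong. Any figure for how far a mean fold rise would shrink describes an analysis that is not in the plan, and it also presumes an older sample for each affected patient. This stands, and no such figure is offered here.

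Other parts of the objection also stand. The documents do not say how many samples were drawn on the vaccination day. A draw on Days 1 to 20 that competes with the protocol sample would be an extra, off-schedule one. SAP 6.11 does not say that unselected samples are left out of the listing. All objectives are exploratory (SAP section 2), endpoint 8 prescribes no statistic, and Protocol 5.11 details only the COVID-19 assays.

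The wording about samples preceding and following the dose does not rescue the rule. It makes the section inconsistent about Day 0, which needs resolving before programming. Nor does the listing settle endpoint 8: SAP 6.10.2.2 plans fold increases and responder counts for COVID-19, while the change tables in SAP 6.2 neither declare nor justify leaving the influenza change underived.

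**Conclusion.** The point holds as a labelling and selection fault. On the literal window wording, every pre-dose sample dated on the vaccination day is labelled Post and selected ahead of the sample taken at 3 weeks or later. This conflicts with the protocol's sampling schedule and with other wording in the same SAP section. The missing 3-week floor is a separate fault that matters only where an early extra sample exists.

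The direct consequence is confined to Pre and Post labels in one exploratory listing. Its extent is unknown because the share of same-day draws is not given. A wrong titre change would arise only if someone later derived it from those labels, and for same-day draws only where an older sample within 183 days is also present. Separately, the influenza part of endpoint 8 has no derived result. The correction is worth making because it is cheap and the samples are already scheduled for collection.

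**What to change.** In SAP 6.11:

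- Treat a sample dated on the vaccination day as Pre unless its recorded time shows that it followed the dose.
- Define Post as the first sample from Day 21 to Day 183 after vaccination and before the next dose. State that the vaccination date is Day 0, since SAP 6.10.3 counts the dose day as Day 1.
- Rewrite the window and selection bullets so that they give the same answer for Day 0.
- Keep draws taken after the dose but before Day 21 in the listing, without the Post label.
- Add an exploratory paired summary per vaccination and per reported titre: number of pairs and geometric mean fold rise with 95% CI, shown when enough pairs exist. The minimum should be stated; the condition of more than 5 datapoints used for later COVID-19 boosters in SAP 6.10.2.2 is one option. The handling of values below the quantification limit in SAP 6.14.6 can be carried over.

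The cost is a few lines of SAP text and one small table, with some programming because seasonal vaccines cover influenza A and B and each reported titre needs its own row. Patients whose only post-vaccination sample is before Day 21 leave the paired summary but remain in the listing.
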